C. Early Stage, Non-Small Cell, Lung Cancer Cases: The table below includes number of patients from 2007 with stage I and II, non-small cell lung cancer entered in each local cancer registry. These data only include patients with tissue proven diagnoses and not those who had CT lesions with extremely high cancer probability and refused surgery or dropped out of follow-up (we did include these patients in our prospective study). Therefore, eligible patients are underestimated while "percent surgery" rates are overestimated when factoring in all patients with early stage, non-small cell disease.

Site	Number of Cases	African-Americans	Percent Surgery
ECU	63	11	70
MCHS	141	24	69
UNC	57	14	74
USC	66	17	75

From our prospective study, we anticipate an average recruitment rate of 70% across sites. Only 11% of all patients approached during the post-diagnosis – pre-treatment recruiting interval refused participation and there was no difference by race.

D. Retrospective Chart Review: Our recently completed study demonstrated that co-morbid

conditions differentially affected black patients' care. Given these data, during the first six months of the intervention trial we will perform a retrospective chart review for the 2008 and 2009 calendar years. We will review all patients diagnosed with stage I or II, non-small cell cancer to serve as a baseline for surgical rates and to examine outcomes of patients treated with and without surgery using a very specific analysis of co-morbid conditions and severity. These data will be checked against Strand's report [45] to assess compatibility and level of detail. The results will be used by our expert panel of co-investigators and site investigators to create an educational checklist to remind lung cancer providers that surgical contra-indications are often relative and subjective. We anticipate the availability of approximately 100-150 charts per site in the 2-year pre-study window. Charts will be selected using appropriate ICD-9 billing codes. Data will be collected in an aggregate manner and no linkage files or specific patient identifiers will be maintained.

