Given the ratio of catchment area patients that receive their lung cancer care at each study site and a conservative, estimated an overall recruitment rate of 50%, we will be able to recruit 165 stage I and II patients per year combining all study sites. We anticipate 3 yrs of patient recruitment with the accrual of 496 patients. We will oversample black patients, as we did in our prospective study, to attain an enrollment goal of 30%.

3. The Interview and Survey Instruments

Patient Interview. We will administer the surveys as face-to-face interviews, conducted by

thoroughly trained RAs at each site. We will attempt to arrange interviews at the convenience of the patient. Before the project begins we will give all RAs a script and provide rigorous training in its use so that interview technique and content will be consistent at all sites; we will also develop and provide training manuals. We will interview patient-participants in private settings. For onsite interviews, we will identify rooms in the same building or adjacent buildings that are apart from clinic. Offsite interview venues will include the investigator's institution, the patients' homes, or other mutually agreeable locations. All interview sites will be private and secure. If patients require more than one sitting to complete the survey because of fatigue or time constraints, we will accommodate such needs.

Patient Questionnaire. The proposed instrument builds on our preliminary work (Appendix E) by formally measuring health literacy. Low literacy likely identifies patients for whom the communication intervention might be more needed and effective. The questionnaire also covers the following constructs and relies on reliable and validated items or batteries drawn from previous instruments. Specifically areas included will be:

1. *Demographic Information:* age, sex (recorded only by interviewers, not asked), marital status, race, educational attainment, estimated household income, type of health insurance, access to a regular source of care, and affiliation with any church or denomination.
2. *Health Status:* Physicians may use poor physical or emotional function as a contraindication for cancer surgery; patients may opt against surgery because of poor health-related quality of life. We will use the SF-12 [23], to assess this domain. (Appendix C)
3. *Health Literacy:* Test of Functional Health Literacy in Adults-short form [61] (Appendix C)

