
hypothesis 1b. the communication intervention will be more effective in patients who score lower in measures of health literacy

Using the logistic regression analyses for clustered data as noted above, the interaction effects of health literacy, S-TOFHLA scores, and intervention group will be tested in all models. . S-TOFHLA scores will be tested as a continuous variable and also, separately, as a dichotomous variable comparing those categorized as inadequate or marginal literacy with those categorized as adequate literacy [103]. Cumulative pre-intervention surgical rates will be compared at all sites with post-intervention rates using Pearson's chi-square test. Post-intervention rates will be compared using test of proportions and changes in proportions from baseline will be compared between surgical and nonsurgical groups using appropriate methods. To determine if the post-intervention rate approaches maximal surgical rates, we will identify patients with high risk co-morbidities, above the age of 80, and need for pneumonectomy or multiple lobectomy in the "no surgery group", subtract this sum from the denominator then re-calculate the surgical rate. We will analyze the secondary specific aim, To measure the effect of the intervention on patients' perceptions of communication and satisfaction with care, by dichotomizing these variables and replacing surgery as the dependent variable in chi-square and logistic regression models as described under the specific aim above.

Specific Aim 2. To reduce the documented difference in lung resection surgery and mortality between African-American and White patients with early stage, non-small cell

lung cancer.

hypothesis 2a. giving physicians who make lung cancer surgery decisions data relating co-morbidity to surgical outcomes will reduce racial differences in surgery

hypothesis 2b. using a real time lung cancer registry to provide physicians race-specific feedback about their surgical treatment of early stage lung cancer patients will reduce racial differences in surgery

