We will analyze patient level cross-sectional dichotomous outcome data using logistic regression growth models. We will both limit analyses to the cancer communicator control group and do an all enrollee analysis by adding a communicator intervention / no communicator intervention predictor variable to the models. First, we will fit a saturated growth model to estimate annual proportions of these outcomes, before and after the registry/feedback intervention, to assess the effects of the intervention on these outcomes by contrasting the proportions before and after the interventions. We will test the null hypothesis that the proportions before and after the intervention are the same. We will repeat this analysis by including "race" and "race x time" interaction in this model to examine changes in these outcomes between the two races and also if there are any differential changes over time. We will test the null hypothesis that the proportions before and after the intervention are the same for each race

Data interpretation: If our data feedback / registry intervention is found to produce an effect in less than the 4 Cancer Centers, it will prompt further examination of the factors that moderate or mediate the relationship between the intervention and completion of cancer treatment. Thus, by conducting an embedded randomized cohort-control study of the Cancer Communicator intervention component, we may be better able to provide more information about the dimensions along which these interventions can or cannot be generalized.

hypothesis 2c. a cancer communicator who utilizes active listening and teach-back methods during discussions about lung cancer surgery with newly diagnosed, early stage patients will increase the rate of surgery in African-American patients more than Caucasian patients compared to usual care.

We will compare post intervention, unadjusted, surgical rates between African-American and White lung cancer patients using chi-square analysis as discussed under Aim 1. We will also perform the maximum rate analysis stratified by race. The regression models described above under Aim 1. We will also apply these analyses to patients in the communicator group alone selecting patients on an intention to treat basis.

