The SF-12 physical and mental component scores will be converted to 0 – 100 scales and utilized as the dependent variable. Baseline scores will be compared first to 6 month scores then 12 month scores using paired t-tests. Generalized linear mixed models for repeated measures data will be constructed in a similar manner as the logistic regression models described above; however, surgical status, race, and comorbid conditions will be forced predictors in these model.

Note that interim analyses regarding specific aims 1 and 2 will be performed at the end of study year 2 then annually. If statistically significant benefits in care are documented on surgical rates and reduction in disparities, the study will be terminated and workshops and individual training sessions of the communication methodologies will be initiated for the care teams at all the study sites.

7. Sample Size

Power computations are computed for post-intervention comparison of proportions. The project anticipates enrolling 496 patients into the study due to constraints on budget, patient availability, and study duration. Thus, we compute the minimal effect size we can detect with statistical power of 80% for our primary aim, AIM 1, using the specified sample size. In computing the effect size, we specify our main outcome as the probability of undergoing surgery for all patients post-baseline as compared to the probability for all patients in the previous study because all groups will receive the data registry and feedback interventions.

Let p_1 be the proportion all patients who undergo surgery in the present study and $p_0 = 0.63$ be the proportion of patients who underwent surgery in the previous study. Using a one-sample test of proportion with 496 subjects overall and significance level of 0.05, we have 80% power to detect a minimally important difference (increase) in surgical rate of $p_0 = 0.63$ to $p_1 = 0.69$. With a sample size of 159 for blacks, we have 80% power to detect an overall increase from $p_0 = 0.55$ (as measured in the previous study) to $p_1 = 0.66$ with significance level of 0.05. With a sample size of 337 for whites, we have 80% power to detect an overall increase from $p_0 = 0.66$ (as measured in the previous study) to $p_1 = 0.73$ with significance level of 0.05.

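### The unadjusted before/after surgery rates compare cohorts with deliberately different race mixes, so on assumed inputs the pooled rate falls about 1.1–1.3 points when nothing has changed

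*SAP*

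**What the plan says.** **Enrolled cohort.** Protocol E.2 (Patient Recruitment): "We will oversample black patients, as we did in our prospective study, to attain an enrollment goal of 30" per cent. SAP section 7 plans slightly more: "With a sample size of 159 for blacks" out of 496, or 32%.

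**Baseline.** Protocol D (Retrospective Chart Review) covers 2008 and 2009: "We will review all patients diagnosed with stage I or II, non-small cell cancer to serve as a baseline for surgical rates". It expects about 100–150 charts per site and mentions no oversampling. It gives no race split. The only one for these sites is in Protocol C: "The table below includes number of patients from 2007 with stage I and II, non-small cell lung cancer entered in each local cancer registry".

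**Unadjusted before/after comparisons.**
- SAP section 6, Aim 1: "Cumulative pre-intervention surgical rates will be compared at all sites with post-intervention rates using" Pearson's chi-square. No stratum, weight or covariate is named.
- SAP section 6, Aim 2: "we will fit a saturated growth model to estimate annual proportions of these outcomes, before and after the registry/feedback intervention", followed by a test that the two proportions are equal. Race and race-by-time enter only when the model is repeated.

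**Where race does enter.** Protocol A (Overview) says the site baseline rates will take account of race and co-morbidity. The repeated Aim 2 model tests before against after within each race. Aim 3 adjusts its before/after analysis for the Aim 1 variables, which include race. However, the forced predictors listed for the Aim 1 model are group, comorbid illnesses and selected baseline scores. Race is not among them, so backward elimination could remove it.

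**The concern.** Race mix differs between the two periods by design, and on the SAP's own figures race is related to surgery. A pooled rate is a weighted average of the race-specific rates, so changing the weights moves it even if no patient's chance of surgery changes. More Black patients in the later period pulls the pooled rate down and offsets part of any real gain.

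At stake is the reading of the registry, feedback and checklist components. Every enrolled patient is exposed to them, so they can be judged only against history. The plan does not say which before/after result governs when the unadjusted and adjusted versions differ. The enriched overall rate also does not describe the sites' actual patient population.

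**Working it through.** **1. The plan's own power figures.** SAP section 7 uses a one-sample test. With two-sided alpha 0.05,

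power = Φ{[(p1 − p0)√n − 1.96√(p0(1 − p0))] / √(p1(1 − p1))}.

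- n = 496, 0.63 to 0.69: 80.0%
- n = 159, 0.55 to 0.66: 80.8%
- n = 337, 0.66 to 0.73: 78.9%

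The stated 80% is reproduced. These figures are not in dispute; they supply the race-specific rates and the 6-point target.

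**2. Inputs for the shift.**
- Baseline Black share (Protocol C, 2007, as a proxy): (11 + 24 + 14 + 17)/(63 + 141 + 57 + 66) = 66/327 = 20.2%. *Assumption:* 2008–2009 was similar.
- Enrolled Black share: 30% (Protocol E.2) or 159/496 = 32.1% (SAP section 7).
- Surgery rates: 0.55 Black and 0.66 White, a gap of 0.11 (SAP section 7, previous study). *Assumption:* these apply to the chart-review population.

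**3. Pooled rate with no real change.** Pooled rate = 0.66 − 0.11 × Black share.

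| Period | Black share | Pooled rate | Change |
|---|---|---|---|
| Baseline | 20.2% | 0.6378 | – |
| Enrolled, goal | 30% | 0.6270 | −1.08 points |
| Enrolled, power section | 32.1% | 0.6247 | −1.31 points |

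A true 6-point rise in each race would appear as 6 − 1.1 = 4.9 or 6 − 1.3 = 4.7 points.

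**4. Sensitivity, one input at a time.** Fall = gap × (enrolled share − baseline share); the two figures are for 30% and 32.1% enrolled.
- Baseline share 17%: 1.43 and 1.66 points. Share 25%: 0.55 and 0.78 points.
- Gap 5 points (share 20.2%): 0.49 and 0.59 points. Gap 15 points: 1.47 and 1.78 points.

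The range is about 0.5–1.8 points.

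**5. Size against sampling error.** Baseline n = 4 × 100 to 4 × 150 = 400–600; enrolled n = 496. SE = √[p̄(1 − p̄)(1/n_pre + 1/496)] = 3.24 points (400 charts) or 2.93 points (600). The shift is therefore 1.08/3.24 = 0.33 to 1.31/2.93 = 0.45 of a standard error. With no real change, the two-sided 5% test would reject about 6.3–7.3% of the time: 5.2–6.5% as a fall and only 0.8–1.1% as a rise.

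**6. Power for a true 6-point rise in each race.** Power = Φ[(d − 1.96·SE_pooled)/SE_unpooled], starting from 0.6378. For example, with 400 charts and d = 0.060, (0.0600 − 1.96 × 0.03157)/0.03167 = −0.06, giving 47.6%.

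| Baseline charts | No shift | 30% Black enrolled | 32.1% Black enrolled |
|---|---|---|---|
| 400 | 47.6% | 34.2% | 31.6% |
| 600 | 55.4% | 40.1% | 37.1% |

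**7. Does stratifying recover it?** Take a 6-point difference in each race, weighted by n_pre·n_post/(n_pre + n_post) within race, as in Mantel-Haenszel. Power is 47.0–47.2% with 400 charts and 54.6–54.9% with 600. The shift is zero and almost no precision is lost.

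**The case against.** The strongest reply is that this is small and partly handled already. Hypothesis 1a is tested by randomised intervention against usual care, and the race mix of a historical baseline cannot bias that. The shift is under half a standard error and works against the intervention, so it cannot create a false success. The Overview, the repeated Aim 2 model and Aim 3 all bring in race. All of this stands. It confines the point to the unadjusted comparisons but does not cure them: the chi-square is still specified as pooled, and race is not protected in the adjusted model.

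The inputs are also proxies. The 20.2% comes from tissue-proven 2007 cases, and the race-specific rates come from another study. That stands too, and is why a range is given.

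A further reply is that race is not the main difference between the periods. Protocol C says registry surgery rates are overestimated because patients without tissue proof are left out, while the trial enrols at a 60% probability of malignancy. The case-weighted registry rate is (63×70 + 141×69 + 57×74 + 66×75)/327 = 71.3%, against 63% in the previous study. Stratifying by race and site would not remove that difference. This is correct and limits what the fix achieves.

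A reader might also infer that SAP section 7 is undermined, because 159 at 0.55 and 337 at 0.66 average 0.625 rather than 0.63, or because the same shift would erode its 80% power. The documents support neither. Rates of 0.554 and 0.664 would print as 0.55 and 0.66 and give (159×0.554 + 337×0.664)/496 = 0.629, so rounding can explain the gap. The 0.63 comes from a previous study that, according to Protocol E.2, also oversampled Black patients, so the move from 20% to 30% does not apply there.

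**Conclusion.** The point holds for the unadjusted historical comparisons only: the pooled chi-square under Aim 1 and the first growth model under Aim 2. Followed as written, they carry a design-induced fall of about 1.1–1.3 points, roughly one fifth of the 6-point rise the SAP treats as minimally important, and lose about 13–18 percentage points of power for such a rise. This rests on an assumed 20% baseline Black share, an 11-point race gap, 400–600 charts and all 496 enrolled patients in the after group.

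It would be going too far to conclude that the trial's randomised result is biased, that all before/after work ignores race, or that the intervention could be made to look effective. This is a moderate weakness worth correcting because the correction is nearly free.

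**What to change.** 1. Replace the pooled chi-square under Aim 1 with a Mantel-Haenszel test and risk difference stratified by race and site.
2. Include race and site in the first Aim 2 growth model, not only in its repeat.
3. Add race to the forced predictors of the adjusted before/after model used for Aim 3.
4. Report the overall post-intervention rate standardised to the baseline race mix, beside the crude rate.
5. Make sure the chart review keeps surgery counts by race and site. Protocol D collects these data in aggregate with no linkage files, so counts not tabulated at the time could not be rebuilt later.
6. State as a limitation that stratification does not remove the eligibility difference between tissue-proven registry cases and the enrolled cohort.

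The cost is SAP wording, a little more analysis, and a baseline table by race and site. Race is already a study variable and the Overview already promises baseline rates that account for it.

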4. *Communication Variables:* The attitudes coupled with Likert-type scales that identified perceptions of communication associated with surgical decisions from the initial study.
5. *Trust:* The Medical Mistrust Index [93]

6-month Telephone Interview

1. Health Status: repeat SF-12
2. Communication Variables as above
3. Patient satisfaction cancer care including the choice of treatment

12-month Telephone Interview. Will repeat 6 month items. To fully assess the importance of lung resection surgery within 4 months of diagnosis, we will determine whether each patient, surgical and nonsurgical, remains alive one year. We will re-administer the SF-12 survey and satisfaction measures by telephone to survivors. We will find patients by maintaining a linkage file that includes best telephone number file, stored separately from original survey information. If the patient is not located at the original number, we will seek current information from the office of their physician or through local phone listings. If a patient surrogate answers the phone, we will seek the patient's availability and clinical status in the conversation with the surrogate.

4. *Interventions – Each site will identify a physician leader to serve as a liaison to the CCE.*
 - A. Cancer Communication – Because of the gaps between documented outcomes of lung cancer surgery and patient communication barriers identified in our recent work, our communication intervention will focus on improving presentation of risk information and confirmation of understanding [13]. Given good post operative outcomes [45, 94] in most patients with significant comorbidities, and the doubling of one-year mortality in our prospective “no surgery” group, patients’ perceptions of worse one-year prognosis with surgery are either misinterpreted or poorly explained. In lung cancer only one-half of patients comprehend proposed treatment within 3 days of their clinical visit and only 40% expressed satisfaction with communication [60]. Moreover, effective communication skills, such as active listening and the teach-back method, which can assist education and confirm understanding are used infrequently in clinical care. For example, Schillinger demonstrated that only 12% of new concepts had confirmation (teach back) by the clinician in encounters for diabetes [59]. Several studies have documented difficulty understanding numbers and calculations, particularly the idea of risk [95].

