Lung Cancer Surgery: Decisions Against Life Saving Care - The Intervention

NCT01687738

Protocol Date: May 13, 2011

Most Recent IRB Approval Date: March 29, 2016

Lung Cancer Surgery: Decisions Against Life Saving Care - The Intervention

STATISTICAL ANALYSES

Outcome Measures

Primary Outcome. Whether or not patients undergo lung resection surgery represents the main study outcome. We will conform to the 4 month standard used in the SEER database. To ascertain the result, we will first call patients' physicians to determine whether surgery occurred within the designated time frame. Given the possibility that individual patients could seek other opinions and receive surgical care elsewhere, when appropriate, we will ask the patient, or a family member (if the patient is dead or unavailable), whether surgery was performed by someone other than the index physician. If surgery has not occurred, we will ask for reasons. Through appropriate consent, we will retain the option of confirmatory medical records review. For secondary analyses, we will record surgeries that occur beyond the 4 month threshold.

Secondary Outcomes.

1. One year, post-enrollment survival in surgical and non-surgical groups
2. Satisfaction of patients that received interventions compared to those who did not
3. Patients' perceptions of communication for those patients that received intervention compared to those who did not
4. SF-12 scores at baseline, 6 months post-enrollment and 12 months post enrollment

6. Data Analysis:

Our current plan includes:

Descriptive statistics (means, standard deviations, frequencies, proportions, correlations, and graphical displays) will be computed for all study variables at baseline and post-baseline. The distribution of all outcome variables will be assessed to determine if distributional assumptions are valid. Descriptive statistics will be obtained for all the variables overall and by race and site. Statistical methods for addressing each of the specific aims of the study are detailed in this section. Since several statistical tests are planned, there is the possibility of incurring spurious results if we do not correct for multiple comparisons. All tests are based on a 2-sided alpha of 0.05.

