The modeling approach will be to initially define as large a maximum model as possible using main effects only (initially no interactions). Preliminary analyses of similar data indicates that the sample size combined with a sufficient number of events (surgery yes) will allow upwards of 30-35 main effects to be included in the model with good reliability for estimation and inference. The generalized estimating equations (GEE) for binary outcomes will be used to fit logistic regression models for clustered data [102]. The primary outcome variable is binary, surgery yes or no, and outcomes of patients clustered within the same site (and/or MD) are expected to be correlated. GEE will allow fitting a logistic regression to the binary outcome while adjusting for the effect of clustering within the same site (and/or MD). As stated previously, independent variables in these analyses will include important demographic variables such as age, race, marital status, household income, health insurance, gender, and education as well as measures of trust, patient satisfaction, functional status, self-reported health, comorbid illness, perceptions of communication, and the communication intervention. The significance of each of the main effects while adjusting for all other effects from the maximum model will be assessed. A backwards elimination approach will, initially, remove effects with a p-value of greater than 0.10. This excludes selected predictors forced predictors into the model (forced predictors include group, comorbid illnesses and selected baseline scores). The reduced model will be refit. Variables have p-values greater than 0.05 will then be removed. The final reduced main effects model, including forced predictors will be refit. Selected interactions will be considered for inclusion into the final reduced main effects model. For the secondary outcomes, survival analysis techniques will be used to assess the one year, post-enrollment survival in surgical and non-surgical groups. Kaplan-Meier curves will be generated. Linear regression models for repeated measures (discrete) outcomes using GEE will be used to assess patient satisfaction of patients that received interventions compared to those who did not, for patients' perceptions of communication for those patients that received intervention compared to those who did not, and for SF12 scores at 6 months post-enrollment and 12 months post enrollment. Covariates will include baseline, group, and other covariates listed above.

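### Satisfaction and perceptions of communication have two unranked, incompatible analyses, and the literacy interaction of hypothesis 1b is tested in two forms, each at 0.05

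*SAP*

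**What the plan says.** Satisfaction and perceptions of communication, each compared between patients who did and did not receive the intervention, are secondary outcomes 2 and 3 (Protocol E.5; SAP, Outcome Measures). SAP section 6 then gives them two analyses.

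- **Under hypothesis 1a:** "Linear regression models for repeated measures (discrete) outcomes using GEE will be used to assess patient satisfaction". The same sentence covers perceptions of communication. The covariates are baseline, group and the variables listed earlier in that section.
- **Under hypothesis 1b:** the secondary aim, "To measure the effect of the intervention on patients' perceptions of communication and satisfaction with care", is to be analysed "by dichotomizing these variables and replacing surgery as the dependent variable in chi-square and logistic regression models".

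No cut-point is given for either outcome, and nothing says which analysis takes precedence.

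For hypothesis 1b, "S-TOFHLA scores will be tested as a continuous variable and also, separately, as a dichotomous variable". The dichotomy sets inadequate or marginal literacy against adequate literacy, with a citation. The interaction of literacy with "intervention group will be tested in all models". Neither coding is named as the main one.

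On error control, the SAP warns that "there is the possibility of incurring spurious results if we do not correct for multiple comparisons", and then states "All tests are based on a 2-sided alpha of 0.05". It names no correction and no order of testing.

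On measurement, Protocol E.3 describes the communication items as "The attitudes coupled with Likert-type scales that identified perceptions of communication associated with surgical decisions from the initial study". They are asked at baseline, 6 months and 12 months. Satisfaction is not in the baseline questionnaire. It is first asked at 6 months and again at 12 months, among survivors.

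**The concern.** The variables and the comparison are the same in both places, so these are two answers to one question. A reader of the final report could not tell from the SAP which result was meant to decide it.

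Two different costs follow. If the dichotomised result decides, the trial uses a less efficient method than one already in its own plan, at a cut-point that can still be chosen after the data are seen. If either result may decide, each question has more than one chance at 0.05. For satisfaction and communication there are three chances per variable: linear GEE, chi-square and logistic regression. For the literacy interaction there are two. What is at stake is the reading of two secondary outcomes and one effect-modification hypothesis.

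**Working it through.** **1. The plan's own power figure.** SAP section 7 states power only for surgery: 80% with N = 496, 0.63 against 0.69, one-sample test, alpha 0.05. With the null variance for the critical value and the alternative variance for power:

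- null SE = √(0.63 × 0.37/496) = 0.0217; alternative SE = √(0.69 × 0.31/496) = 0.0208
- power = Φ[(0.06 − 1.96 × 0.0217)/0.0208] = 80.0%, two-sided

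The figure reproduces. It says nothing about satisfaction, communication or the literacy interaction, for which no power is stated.

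**2. Assumptions needed beyond the documents.** The documents give no SD, effect size, cut-point, allocation ratio or dropout for these outcomes. I assume 1:1 allocation (496/2 = 248 per arm), a normally distributed score, one time point and two-sided 0.05.

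**3. Power if the dichotomised version is definitive.** The standardised difference with 80% power on the full scale is d = (1.960 + 0.842) × √(2/248) = 0.25.

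Cut the score at quantile q, with c = Φ⁻¹(q). The proportions above the cut are 1 − Φ(c + d/2) and 1 − Φ(c − d/2). Efficiency relative to the full scale is φ(c)²/[q(1 − q)]. At the median this is 0.399²/0.25 = 0.64. Power comes from the usual two-proportion test.

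| Cut | Proportions above cut | Relative efficiency | Power | Per arm for 80% |
|---|---|---|---|---|
| none | – | 1 | 80% | 248 |
| 50/50 | 0.450 v 0.550 | 0.64 | 61% | 391 |
| 70/30 | 0.258 v 0.345 | 0.58 | 56% | 433 |
| 80/20 | 0.167 v 0.237 | 0.49 | 50% | 510 |
| 90/10 | 0.080 v 0.124 | 0.34 | 37% | 733 |

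With an assumed 15% or 25% loss to follow-up (211 or 186 per arm), the effect with 80% power on the full scale rises to d = 0.27 or 0.29. Power with a median cut stays at about 61%.

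**4. False positives if either form may count.** Under the null, the correlation between the full-scale and the dichotomised statistic is ρ = φ(c)/√[q(1 − q)]. The chance that at least one exceeds 1.96 in absolute value, from the bivariate normal, is:

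| Cut | ρ | P(at least one significant) |
|---|---|---|
| 50/50 | 0.80 | 7.8% |
| 70/30 | 0.76 | 8.1% |
| 80/20 | 0.70 | 8.4% |
| 90/10 | 0.59 | 8.8% |

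For two independent tests it would be 1 − 0.95² = 9.75%, which these correlated pairs do not reach. The same calculation serves as an approximation for S-TOFHLA by arm. The share of patients with low literacy is not in the documents, hence the range. Three tests per variable would be bounded by 1 − 0.95³ = 14.3%. The true figure is lower, because the three are strongly related.

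**5. Can the linear model be adopted as it stands?** No. Its covariates include a baseline value, but satisfaction has none. The earlier list that it refers to contains patient satisfaction and perceptions of communication. Read literally, each outcome is adjusted for itself or for the other, and both may be affected by the intervention. Nor is a 6-month or 12-month contrast named.

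**The case against.** The strongest reply is that the efficient analyses are already in the plan, so nothing is lost unless the dichotomised result is treated as definitive. That is correct, and the power figures above are conditional on it. It does not close the point, because the SAP makes dichotomising the stated method for the secondary aim and nowhere calls it supportive.

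Several stronger readings are tempting, and the documents do not support them.

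- **496 patients act like about 316.** The arithmetic (496 × 0.637) assumes a normal score, a median split and complete follow-up. No median split is mentioned, the communication items are Likert-type, and only survivors are surveyed at 12 months. For such scores the loss depends on the distribution and on where the cut falls.
- **The literacy cut-point is open after the data are seen.** It is not, since the split uses named, cited categories. The complaint there is two unranked tests only. One could read the dichotomous form as supportive, but no ranking is written.
- **The investigators will report whichever form is significant.** Nothing says so. The SAP leaves room for it, and it raises multiple comparisons itself. The missing correction is a gap across the whole plan, and this is one small instance of it.

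The chi-square test also has a merit that should be kept in view: it is an unadjusted randomised comparison, which the linear model as now specified is not.

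**Conclusion.** The point holds as an inconsistency to resolve, and it is minor. The SAP gives incompatible analyses of satisfaction and of perceptions of communication by arm, with no cut-point and no precedence. It also tests the hypothesis 1b interaction in two unranked forms, each at two-sided 0.05.

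The size depends on which way the ambiguity falls. If dichotomised outcomes decide, power drops from 80% to about 61% (median cut) or about 50% (80/20 cut), under a normal score and 248 per arm. If either form may count, a full-scale and dichotomised pair carries about 8 to 9% false-positive risk per question under similar assumptions. These figures are illustrations under stated assumptions and cannot be derived from the documents.

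A reader might infer that the trial's main result is weakened. It is not. The stated power concerns surgery alone, and the early-termination rule in SAP section 6 rests on surgical rates and disparities.

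**What to change.** Amend the SAP text under hypothesis 1b as follows.

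- **Satisfaction and communication:** make the full-scale repeated-measures comparison by randomised arm the single definitive analysis of each, and name the time-point contrast to be tested.
- **Covariates:** adjust for the baseline score only where it is collected (communication, not satisfaction). Exclude post-randomisation satisfaction and communication measures from the covariates.
- **Hypothesis 1b:** make the continuous S-TOFHLA by arm interaction the definitive test.
- **Dichotomised versions:** keep them, labelled as supportive, with the satisfaction and communication cut-points fixed in advance. The S-TOFHLA categories can stay as written.

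The sentence under hypothesis 1a should be aligned with this. The cost is SAP wording and a slightly less simple presentation. No new data, patients or procedures are needed.
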